## **REVISION HISTORY**

Version Number	Version Date	Summary and Rational of Revision(s)
Final 1.0	12 April 2018	There are no revisions as this is the first final version.

## LIST OF ABBREVIATIONS AND DEFINITION OF TERMS

Abbreviation	Definition
AE	Adverse event
ALT	Alanine transaminase
ANCOVA	Analysis of covariance
apo(a)	Apolipoprotein(a)
apoB	Apolipoprotein B
ASO	Antisense oligonucleotide
ASGPR	Asialoglycoprotein receptor
AST	Aspartate transaminase
ATC	Anatomical therapeutic chemical
BMI	Body mass index
BUN	Blood urea nitrogen
CAD	Coronary artery disease
CI	Confidence interval
CKD-EPI	Chronic Kidney Disease –Epidemiological Collaboration
CSR	Clinical study report
CTCAE	Common Terminology Criteria for Adverse Events
CVD	Cardiovascular disease
ECG	Electrocardiogram
eCRF	Electronic case report form
ET	Early Termination
FAS	Full analysis set
FLR	Flu-like Reaction
GalNAc3	N -acetyl galactosamine
GFR	Glomerular Filtration Rate
ICH	International Conference on Harmonisation
IEC	Independent Ethics Committee
IM	Immunogenicity
INR	International normalized ratio
IRB	Institutional Review Board
ISIS 681257	Antisense inhibitor of apolipoprotein (a)
ITT	Intent-to-treat
IXRS	Interactive Web-Response System
LCRIS	Local Cutaneous Reaction at the Injection Site
LDL	Low density lipoprotein
LDL-C	Low density lipoprotein cholesterol
LLN	Lower limit of normal
Lp(a)	Lipoprotein(a)

Abbreviation	Definition
MCMC	Markov Chain Monte Carlo
MedDRA	Medical Dictionary for Regulatory Activities
mRNA	Messenger ribonucleic acid
n	Number of patients
OxPL	Oxidized phospholipids
OxPL-apo(a)	oxidized phospholipids on apolipoprotein(a)
OxPL-apoB	oxidized phospholipids on apolipoprotein B
PAD	Peripheral arterial disease
PK	Pharmacokinetic
PKS	Pharmacokinetic set
PPS	Per-protocol set
PT	Preferred term
Rel Day	Relative study day
SAP	Statistical analysis plan
SC	Subcutaneous
SD	Standard deviation
SI	Système International (International System of Units)
SNP	Single nucleotide polymorphism
SOC	System organ class
SUSAR	Suspected unexpected serious adverse reaction
TEAE	Treatment-emergent adverse event
UACR	Urine albumin/creatinine ratio
ULN	Upper limit of normal
UPCR	Urine protein/creatinine ratio
WBC	White blood cell (count)
WHO	World Health Organization

## **1. INFORMATION FROM THE STUDY PROTOCOL**

### **1.1. Introduction and Objectives**

#### **1.1.1. Introduction**

Lipoprotein(a) [Lp(a)] is an atherogenic lipoprotein in which the apolipoprotein B (apoB) component of low density lipoprotein (LDL) is linked by a disulfide bond to apolipoprotein(a) [apo(a)], the distinct protein component of Lp(a) that is mainly responsible for its signature structural and functional properties (Dubé et al. 2012; Kronenberg and Utermann 2013). Lp(a) is now recognized as an independent, genetic, causal risk factor for coronary artery disease (CAD), stroke, peripheral arterial disease (PAD), and calcific aortic stenosis (Erqou et al. 2009; Nordestgaard et al. 2010; Thanassoulis et al. 2013).

Therapeutic modalities to reduce Lp(a) levels in humans are few, and there are no drugs currently available that specifically target Lp(a) alone. Antisense oligonucleotides (ASOs) are emerging as viable therapeutic agents to treat disorders where overexpression of proteins is associated with a disease process. Apo(a) is synthesized primarily in the liver, a target organ for ASOs, where it is subsequently covalently linked to the apoB-100 component of LDL to form the Lp(a) lipoprotein. The goal of treatment with ISIS 681257 [antisense inhibitor of apolipoprotein (a)] is to reduce the production of apo(a) in the liver and thus, the level of Lp(a) lipoprotein by using an ASO directed against the messenger ribonucleic acid (mRNA) of apo(a). It has been hypothesized that a pharmacologic reduction in Lp(a) could slow down or reverse CVD by reducing thrombotic, atherogenic, or inflammatory events in patients with elevated Lp(a) levels (Nordestgaard et al. 2010).

#### **1.1.2. Study Objectives**

This statistical analysis plan (SAP) is designed to outline the methods to be used in the analysis of study data in order to answer the study objective(s). Populations for analysis, data handling rules, statistical methods, and formats for data presentation are provided. The statistical analyses and summary tabulations described in this SAP will provide the basis for the results sections of the clinical study report (CSR) for this trial.

This SAP will also outline any differences in the currently planned analytical objectives relative to those planned in the study protocol.

##### **1.1.2.1. Primary Objective**

To evaluate the safety and tolerability of ISIS 681257 and to assess the efficacy of different doses and dosing regimens of ISIS 681257 for reduction of plasma Lp(a) levels in patients with hyperlipoproteinemia(a) and established cardiovascular disease (CVD).

##### **1.1.2.2. Secondary Objectives**

To evaluate the efficacy of ISIS 681257 on plasma levels of low density lipoprotein cholesterol (LDL-C), apoB, oxidized phospholipids (OxPL) on apo(a) [OxPL-apo(a)] and OxPL on apoB (OxPL-apoB).

To evaluate pharmacokinetics (PK) of ISIS 681257 across different doses and dose regimens in patients with hyperlipoproteinemia(a) and established CVD.

## 1.2. Study Design

### 1.2.1. Synopsis of Study Design

This is a multicenter, randomized, double-blind, placebo-controlled, dose-ranging study. ISIS 681257 (or placebo) will be administered subcutaneously (SC) every week, every 2 weeks, or every 4 weeks, depending on cohort assignment, for up to 52 weekly doses, up to 26 every 2-week doses, or up to 13 every 4-week doses. Minimum treatment duration is 6 months, maximum treatment duration is 12 months.

The primary analysis time point is at Week 25 for patients who received every 4-week dosing (Cohorts A-C) and at Week 27 for patients who received 2-week or weekly dosing (Cohorts D and E). For patients continuing treatment beyond the primary analysis time point additional supportive efficacy analysis (to evaluate whether the treatment effect is maintained) and safety analysis (for the purpose of dose(s) selection) will be repeated at the completion of Study Drug treatment. A description of each cohort is presented in [Table 1](#).

**Table 1: Study Drug Dosing Information**

Cohort	Treatment	Volume to Administer/Dose	# Doses	Total ISIS 681257
A	20 mg ISIS 651257 or placebo (every 4 weeks)	0.2 mL	≤ 13	≤ 260 mg
B	40 mg ISIS 651257 or placebo (every 4 weeks)	0.4 mL	≤ 13	≤ 520 mg
C	60 mg ISIS 651257 or placebo (every 4 weeks)	0.6 mL	≤ 13	≤ 780 mg
D	20 mg ISIS 651257 or placebo (every 2 weeks)	0.2 mL	≤ 26	≤ 520 mg
E	20 mg ISIS 651257 or placebo (every week)	0.2 mL	≤ 52	≤ 1040 mg

The treatment portion of the study will be complete when the last enrolled patient reaches 6 months of exposure. All patients still on treatment will have their last dose taken as scheduled, and they will enter a 16-week post-treatment follow-up period at one dosing interval post last dose. Accordingly, for each treatment cohort treatment period is defined as the time from the first dose through one dosing interval post last dose.

Patients  $\geq 18$  and  $\leq 80$  years old with elevated plasma Lp(a) levels ( $\geq 60$  mg/dL ) and a clinical diagnosis of CVD are eligible for enrollment upon meeting the study specific eligibility criteria. Patients will be on standard-of-care preventative therapy for other than elevated Lp(a) CVD risk factors as per current guidelines.

Clinical diagnosis of CVD is defined as documented CAD, stroke, or PAD. A diagnosis of CAD has to be documented by any of the following:

- Angiographic evidence of  $\geq 50\%$  stenosis of 1 or more major epicardial coronary arteries.

- History of myocardial infarction documented by positive enzymes, and either symptoms of myocardial ischemia, or electrocardiogram (ECG) changes (Thygesen et al. 2012).
- History of coronary revascularization.
- Evidence of cardiac ischemia on exercise testing, or imaging study.

Patients will be evaluated for study eligibility during Screening, which takes place within 4 weeks prior to Day 1 (the first day of Study Drug administration). Patients who are determined to be eligible, based on screening assessments, will be enrolled in the study at Day 1 and randomly assigned to 1 of the 5 parallel dosing cohorts, with each cohort having a 5:1 ratio to receive ISIS 681257 or matching volume of placebo, respectively, by SC injection for up to 52 weeks.

The length of patients' participation in the study may be up to 72 weeks, which includes a 4-week screening period, an up to 52-week treatment period with Study Drug (ISIS 681257 or placebo), and a 16-week post-treatment follow-up period. The treatment portion of the study will be complete when the last enrolled patient reaches 6 months of exposure.

Patients may be required to attend additional visits for monitoring of adverse events (AEs) or abnormal investigation results. The frequency of additional monitoring will be determined by the Study Medical Monitor in consultation with the Investigator.

The independent Data Safety Monitoring Board (DSMB) will oversee the safety, tolerability, efficacy (when needed) and the overall conduct of the study.

#### 1.2.2. Randomization Methodology

Patients will be randomized after all screening assessments have been completed and after the Investigator has verified that they are eligible per criteria in Protocol Sections 5.1 and 5.2. No patient may begin treatment prior to randomization and assignment of a unique patient identification number.

Using an Interactive Web-Response System (IXRS), eligible patients will be randomized in a 1:1:1:1:1 ratio to 1 of the 5 parallel-dose cohorts (Cohorts A, B, C, D, or E). Within each dose cohort, patients will be randomized in a 5:1 ratio to receive ISIS 681257 or matching volume of placebo, respectively. A permuted block schedule will be used. The randomization schedule will be generated and held by the Unblinded Biostatistician at [REDACTED].

#### 1.2.3. Stopping Rules and Unblinding

The Sponsor and all patients, monitors, and Study Center personnel related to the study will be blinded throughout the study and until all patients have completed the study and the database has been locked. However, if a patient has suffered a serious AE (as defined in Protocol Section 9.3.3), and/or when knowledge of the treatment assignment will impact the clinical management of the patient, the Investigator will have the ability to unblind the treatment assignment for that patient using the IXRS. The Sponsor will determine the point at which all treatment assignments will be unblinded. The Sponsor or designee will be informed of the unblinding of a patient within 24 hours. In addition, all suspected unexpected serious adverse reactions (SUSARs) will be unblinded by the Sponsor's or designee's Drug Safety and Quality Assurance personnel for the purpose of regulatory reporting (see Protocol Section 9.2).

The Investigator may interrupt or permanently discontinue study treatment for any medical reason including changes in clinical laboratory results. In the event of an initial clinical laboratory result that meets a stopping criterion, patients must not be re-dosed until a confirmatory test result has been reviewed by the Study Medical Monitor. If any of the stopping criteria described below are met and are confirmed, the patient will be permanently discontinued from further treatment with ISIS 681257 or placebo:

- 1) Liver chemistry elevations.
- 2) Renal function test results.
- 3) Platelet count results.

For more details on the criteria of stopping rules, refer to Protocol Section 8.6.

#### 1.2.4. Study Procedures

The schedule of procedures for all cohorts can be found in Appendix A of the study protocol.

#### 1.2.5. Efficacy and Safety Parameters

##### 1.2.5.1. Primary Efficacy Parameters

The primary efficacy endpoint is the percent change in Lp(a) from baseline at the primary analysis time point achieved by ISIS 681257 compared to placebo.

##### 1.2.5.2. Secondary Efficacy Parameters

The secondary endpoints include the following parameters from baseline at the primary analysis time point for ISIS 681257 compared to placebo:

- Percent change from baseline in LDL-C.
- Proportion of patients who achieve plasma Lp(a)  $\leq 125$  nmol/L ( $\leq 50$  mg/dL).
- Proportion of patients who achieve plasma Lp(a)  $\leq 75$  nmol/L ( $\leq 30$  mg/dL)
- Percent change from baseline in apoB.
- Percent change from baseline in OxPL-apo(a).
- Percent change from baseline in OxPL-apoB.

##### 1.2.5.3. Safety Parameters

The safety analysis will be performed using the following parameters:

- AEs.
- Vital signs and weight.
- Physical examinations.
- Clinical laboratory tests (serum chemistry, hematology, coagulation, urinalysis).
- Proportion of patients with platelet drop by severity, including platelet drop below lower limit of normal (LLN), platelet drop greater than 30% from baseline, or any platelet drop meeting stopping rules.

- Proportion of patients with liver AEs by severity, number of patients meeting liver stopping rules, and change in liver function tests by severity.
- Proportion of patients with renal events by severity, number of patients meeting renal stopping rules, and change in renal function tests by severity.
- ECGs.
- Use of concomitant medications.

## **2. PATIENT POPULATION**

### **2.1. Population Definitions**

The following patient populations will be evaluated and used for presentation and analysis of the data:

- **Safety Set:** All patients who are randomized and receive at least 1 dose of Study Drug. This population will be used for all safety analyses.
- **Full Analysis Set (FAS):** All patients who are randomized and received at least 1 dose of Study Drug (ISIS 681257 or placebo). The FAS represents the practically-feasible intent-to-treat (ITT) population as delineated in International Conference on Harmonisation (ICH) Guideline E9. This population will be used for the primary analysis of efficacy.
- **Per-Protocol Set (PPS):** Subset of the FAS who have a baseline assessment for lipids, received within 6 months at least 5 out of 6 monthly doses of Study Drug for patients randomized in Cohorts A, B, and C, at least 11 out of 13 planned every-2-week doses for patients randomized in Cohort D, or at least 22 out of 26 planned weekly doses for patients randomized in Cohort E, and who have no major protocol deviations that would be expected to affect efficacy assessments. This population will be used for supportive inferences concerning efficacy.
- **Pharmacokinetic Set (PKS):** All patients who are randomized and received at least 1 dose of active Study Drug (ISIS 681257), and have at least 1 evaluable PK data. This population will be used for analysis of PK data.

### **2.2. Protocol Deviations**

The list of prespecified major deviations is provided in the [Appendix 2](#) of the SAP. All protocol deviations that could compromise the interpretation of efficacy or safety of the study drug will be considered as major deviations. The Sponsor or designee will be responsible for producing the final protocol deviation file (formatted as a Microsoft Excel file), in collaboration with [REDACTED] and the data monitoring group as applicable; this file will include a description of the protocol deviation and clearly identify whether or not this deviation warrants exclusion from the PPS. This file will be finalized prior to database lock for the primary analysis.

All protocol deviations will be presented in a data listing.

### **3. GENERAL STATISTICAL METHODS**

#### **3.1. Sample Size Justification**

Based upon prior clinical trial experience with ISIS 681257, it is estimated that the standard deviation (SD) of the percent change in Lp(a) is approximately 20%. With 23 patients in each ISIS 681257 treatment group and 23 in placebo group there would be approximately 90% power to detect a 20% difference in percent change in Lp(a) levels between the ISIS 681257 treatment groups and placebo group at an alpha level of 0.05, assuming 30% reduction in the ISIS 681257 patients and 10% reduction in the placebo patients.

Based upon prior clinical trial experience with Ionis ASOs, assuming the incidence rate of platelet count below LLN in placebo-treated patients is 1.9%, in the ISIS 681257-treated patients is 3.8%, twice the incidence rate observed in placebo, with 45 patients in each ISIS 681257 treatment group, there would be approximately 80% probability of observing at least 1 event.

Therefore, approximately 270 patients (54 patients per cohort, including 45 patients per cohort treated with ISIS 681257), will be randomized to ensure that both the safety and efficacy of ISIS 681257 will be adequately characterized in the study.

#### **3.2. General Methods**

All data listings that contain an evaluation date will contain a relative study day (Rel Day). Pre-treatment and on-treatment study days are numbered relative to the day of the first dose of study medication which is designated as Day 1. The preceding day is Day -1, the day before that is Day -2, etc. The last day of study medication is designated with an "L" (eg, Day 14L).

All output will be incorporated into Microsoft Word or Excel files, or Adobe Acrobat PDF files, sorted and labeled according to the ICH recommendations, and formatted to the appropriate page size(s).

All electronic case report form (eCRF) data, lab data transfers, and any outcomes derived from the data will be provided in the patient data listings. Patient data listings will be presented for all patients enrolled into the study. Descriptive summary statistics including number of patients (n), mean, median, SD, standard error, interquartile range (25th percentile, 75th percentile), and range (minimum, maximum) for continuous variables, and counts and percentages for categorical variables will be used to summarize most data. A 'Missing' category may be presented, if warranted. Where appropriate, p-values will be reported.

Assuming raw or derived variables are to 'x' decimal places, the data will be presented as follows:

- Range to x decimal places
- Mean and median to (x+1) decimal places
- SD to (x+2) decimal places
- (x+2) should not be greater than 4 decimal places
- percentages may be calculated without a decimal place or with (x+1) decimal place

Presentation of pharmacokinetic data will be separately defined in the TFL shells.

Formal statistical hypothesis testing will be performed on the primary and select secondary efficacy endpoints, with all tests conducted at the 2-sided and 5% Type I error rate unless otherwise stated. Summary statistics will be presented, as well as confidence intervals (CIs) on selected parameters, as described in the sections below.

### **3.3. Computing Environment**

All descriptive statistical analyses will be performed using SAS statistical software v9.3, unless otherwise noted. Medical history and AEs will be coded using the Medical Dictionary for Regulatory Activities (MedDRA) v20.0. Concomitant medications will be coded using the World Health Organization (WHO) Drug Dictionary version March 2017.

### **3.4. Baseline Definitions**

Baseline for Lp(a), LDL-C, apoB, OxPL-apo(a), OxPL-apoB, and other lipid measurements will be defined as the pre-dose measurement on Day 1 or closest to Day 1, prior to administration of Study Drug. The baseline for platelet count is defined as the average of all platelet count data points prior to the first dose of the study drug. The baseline for other measurements is defined as the last non-missing assessment prior to the first dose of study drug.

### **3.5. Methods of Pooling Data**

Data from patients who receive placebo will be pooled for analysis. For the primary and secondary efficacy endpoints, the primary analysis timepoint will combine Week 25 for patients who received every 4-week dosing (Cohorts A-C) and Week 27 for patients who received every 2-week or weekly dosing (Cohorts D and E). For all other parameters, pooling will be based on the data available at each visit per the schedule of procedures in the Study Protocol.

In addition to being pooled for analysis, patients who receive placebo will also be compared with patients receiving ISIS 681257 on a within-cohort basis. Details can be found in [Section 4](#).

Data from patients who receive ISIS 681257 will be pooled in summary tabulations, where appropriate.

### **3.6. Adjustments for Covariates**

Baseline Lp(a), LDL-C, apoB, OxPL-apo(a), and OxPL-apoB will act as covariates in their respective analyses using an analysis of covariance (ANCOVA) model.

### **3.7. Multiple Comparisons/Multiplicity**

A multiple testing procedure will not be used for this study with a single primary efficacy endpoint.

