## **4. STUDY ANALYSES**

Treatment groups are ISIS 681257 treatment groups and pooled placebo group. ISIS 681257 treatment groups include:

ISIS 681257 20 mg (Every 4 weeks)

ISIS 681257 40 mg (Every 4 weeks)

ISIS 681257 60 mg (Every 4 weeks)

ISIS 681257 20 mg (Every 2 weeks)

ISIS 681257 20 mg (Every week)

Within cohort comparisons between patients receiving ISIS 681257 and patients receiving placebo will be performed for selected safety endpoints, as appropriate.

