#### **4.3.1. Analysis of the Primary Efficacy Endpoint**

As described in Section 1.2.5, the primary efficacy endpoint is the percent change in fasting Lp(a) from baseline at the primary analysis time point (Week 25 for patients in Cohorts A-C; Week 27 for patients in Cohorts D-E) achieved by ISIS 681257 compared to placebo.

The percent change from baseline in Lp(a) will be analyzed using an ANCOVA model with treatment group as factors and log-transformed baseline Lp(a) as covariate. The ANCOVA model will use  $\log(Y/X)$  as dependent variable, where Y is the post-baseline value of Lp(a) and X is the baseline value of Lp(a). The model will provide an estimate of the log ratio, which will then be converted back to the original ratio scale. The percent change from baseline will then be estimated based on the estimated ratio. Patients with missing primary endpoint will have their fasting Lp(a) value imputed using the multiple imputation method described in Section 3.10.1.

The primary endpoint will be compared between ISIS 681257 treatment groups and the pooled placebo group for each of the 100 imputed datasets. The estimates from the 100 fitted models will be combined to provide an overall estimate, with corresponding CIs and p-value (Little and Rubin, 2002). Results from the ANCOVA model will be tabulated by ISIS 681257 treatment groups compared to the pooled placebo group.

Mean (SD) percent change over time in fasting Lp(a) will be plotted by ISIS 681257 treatment group and pooled placebo group, until there are fewer than 10% of the FAS/PPS population at a given visit. Waterfall plots of by-patient percent changes from baseline to the primary analysis time point will also be provided.

The primary efficacy analysis will take place after the last patient has completed the primary analysis time point, and the database has been locked.

All primary efficacy data will be provided in data listings.

The primary efficacy analysis will be done using the FAS population.

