#### 4.3.2. Analysis of the Secondary Efficacy Endpoints

##### 4.3.2.1. Percent Change from Baseline in fasting LDL-C

The percent change from baseline at the primary analysis time point in fasting LDL-C will be compared between each ISIS 681257 treatment groups and the pooled placebo group using an ANCOVA model with treatment groups as factors and log-transformed baseline LDL-C values as covariate. Similar to the primary endpoint, the ANCOVA model will use  $\log(Y/X)$  as dependent variable, where Y is the post-baseline value of LDL-C and X is the baseline value of LDL-C. Corresponding 95% CIs and p-value will be provided.

Mean (SD) percent change over time in fasting LDL-C will be plotted by ISIS 681257 treatment group and pooled placebo group, until there are fewer than 10% of the FAS/PPS population at a given visit. Waterfall plots of by-patient percent changes from baseline to the primary analysis time point will also be provided.

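### SAP Section 3.7 waives multiplicity control because there is one primary endpoint, but that reason does not cover five formal regimen-versus-placebo tests, whose family-wise error reaches about 18% if no regimen works

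*SAP*

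**What the plan says.** Section 3.7 of the SAP is a single sentence: "A multiple testing procedure will not be used for this study with a single primary efficacy endpoint". It does not mention the number of regimens.

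Section 3.2 announces formal hypothesis testing for the primary endpoint and for some of the secondary endpoints, "with all tests conducted at the 2-sided and 5% Type I error rate unless otherwise stated".

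Section 4 sets the comparison structure: "Treatment groups are ISIS 681257 treatment groups and pooled placebo group". It then lists five active groups: 20, 40 and 60 mg every 4 weeks, 20 mg every 2 weeks, and 20 mg every week.

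Section 4.3.1 applies this structure to the primary endpoint: "The primary endpoint will be compared between ISIS 681257 treatment groups and the pooled placebo group for each of the 100 imputed datasets". The 100 fits are combined into an overall estimate with confidence intervals and a p-value, and "Results from the ANCOVA model will be tabulated by ISIS 681257 treatment groups compared to the pooled placebo group". Section 4.3.2.1 is explicit for LDL-C, which "will be compared between each ISIS 681257 treatment groups and the pooled placebo group using an ANCOVA model".

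The power statement in Section 3.1 concerns one active group against placebo, "at an alpha level of 0.05, assuming 30% reduction in the ISIS 681257 patients and 10% reduction in the placebo patients".

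**The concern.** The number of endpoints and the number of tests are different things. The primary analysis has one endpoint and five contrasts against a shared control, each of which can give a false positive. The SAP provides nothing that would make one contrast the confirmatory one: no overall test first, no fixed sequence, no named primary regimen, no dose-response trend test. It also does not call the efficacy p-values exploratory or nominal.

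A reader of Section 3.7 would conclude that multiplicity had been considered and did not arise. Five unadjusted p-values and confidence intervals would then be reported as formal 5% results, with no rule set in advance for saying which regimens were shown to work.

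**Working it through.** **Inputs**
- Five active groups and one pooled placebo group (Section 4).
- Randomization 1:1:1:1:1 to cohorts and 5:1 within cohort (Section 1.2.2), with 54 patients per cohort and 45 of them active (Section 3.1). Pooled placebo is therefore 5 × (54 − 45) = 45, and the total is 5 × 45 + 45 = 270, as stated.
- SD 20 points, difference 20 points (30% against 10% reduction), 23 per group, power about 90%, alpha 0.05 (Section 3.1).
- Each test two-sided at 5% (Section 3.2).

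**1. The SAP's own power figure.** Two-sample t test with n = 23 per group: noncentrality = (20/20) × √(23/2) = 3.39, df = 44. Power is 91.2%, which agrees with the stated value of about 90%. This is the power of one unadjusted comparison.

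**2. Correlation between contrasts.** Contrasts that share a control have correlation n_active/(n_active + n_placebo) = 45/(45 + 45) = 0.5.

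**3. Family-wise error.** Residual df = 270 − 7 = 263 (six group means and one covariate), and the unadjusted critical value is 1.969. For k inert regimens, the chance that at least one |t| exceeds 1.969 comes from integrating the multivariate t distribution with correlation 0.5:

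| Inert regimens | Any false positive | Any false claim of benefit |
|---|---|---|
| 1 | 5.0% | 2.5% |
| 2 | 9.1% | 4.5% |
| 3 | 12.5% | 6.3% |
| 4 | 15.5% | 7.8% |
| 5 | 18.2% | 9.1% |

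A simulation of 400,000 trials with all five inert also gives 18.2%. For reference, five independent tests would give 1 − 0.95⁵ = 22.6%, and the Bonferroni bound is 5 × 5% = 25%.

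**4. Critical value for 5% family-wise.** Solving for the value that |t| exceeds at least once in five contrasts with probability 0.05 gives 2.53 (Dunnett, 263 df), a per-comparison two-sided alpha of 0.0121.

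**5. Power per regimen on the planning effect** (difference 20, SD 20):

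| Patients per group | Noncentrality | Unadjusted | Dunnett |
|---|---|---|---|
| 45 v 45, 263 df | √(45/2) = 4.74 | 99.7% | 98.6% |
| 23 v 23 | √(23/2) = 3.39 | 91.2% (44 df) | 77.6% (44 df) to 80.0% (131 df) |

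The range in the last cell depends on whether the residual variance comes from the two groups compared (44 df) or from all six groups of 23 (6 × 23 − 7 = 131 df). If each 45 v 45 contrast used only its own two groups, Dunnett power would be 98.4%.

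**The case against.** The strongest reply is that the SAP attaches 5% to each test, each test does keep 5%, and Section 3.7 openly says that nothing is adjusted. That is correct. A reader might infer that the SAP's stated 5% is really 18%, but the SAP never states a family-wise rate. The fault is a reason that does not apply to the multiplicity present, and silence about the rate that results.

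Three other stronger readings also go too far.
- A reader might say that the chance of declaring an ineffective regimen effective is 18%. That figure is two-sided and includes regimens found worse than placebo. In the benefit direction it is 9.1%, against 2.5% for one test. Both values need all five regimens to be inert. The SAP plans on a 30% reduction on drug and cites earlier experience with the compound, so this is a worst case.
- A reader might infer that the smallest efficacy p-value will choose the dose. The SAP does not say so. Section 1.2.1 links dose selection to the safety analysis.
- A reader might count 30 further formal tests (six secondary endpoints by five regimens). Section 3.2 limits formal testing to selected secondary endpoints. P-values are promised for LDL-C, apoB, OxPL-apo(a) and OxPL-apoB, which makes 4 × 5 = 20 contrasts. Section 4.3.2.2 compares the two responder endpoints without mentioning a p-value. None of these tests enters the 18%.

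It can also be argued that a dose-ranging study needs no family-wise control. That is a defensible position, but the SAP does not take it: Section 3.2 calls the tests formal, and Section 3.7 gives a different reason.

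**Conclusion.** The point holds. The single-endpoint rationale does not address five regimen-versus-placebo tests, and nothing else in the SAP does. With 45 per group, family-wise error runs from 5% with one inert regimen to about 18% with five, or from 2.5% to about 9% for false claims of benefit.

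These figures assume 45 evaluable patients per group and equal variances. Equal dropout across groups leaves the correlation at 0.5 and the result essentially unchanged. The power figures use the SAP's untransformed percent-change scale, whereas the model in Section 4.3.1 analyses the log ratio to baseline, so they show the cost on the planning assumptions only.

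If the drug works as planned, the primary conclusions are unlikely to change. The change should be made because it is cheap and settles in advance how the five results are to be read; the trial's validity does not depend on it.

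**What to change.** 1. In Section 3.7, delete the single-endpoint rationale and name the five primary contrasts as the family.
2. In Section 4.3.1, report Dunnett-adjusted p-values and simultaneous 95% confidence intervals for those contrasts, with unadjusted values alongside if wanted. Because the result combines 100 imputed-data ANCOVAs, adjusted p-values should not be averaged across datasets. Pool the five contrasts and their covariance matrix first, then apply one simultaneous critical value (about 2.53 at the planned sizes).
3. Label the secondary p-values nominal.
4. In Section 3.1, either say that the 90% at 23 per group refers to a single unadjusted test, or restate power for 45 per group.

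If the sponsor prefers unadjusted tests, Section 3.7 should say that the five regimen-versus-placebo p-values are nominal and not controlled family-wise, and the formal-testing wording in Section 3.2 should be brought into line.

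**Cost:** a few sentences, a modest amount of programming for the pooled covariance, and wider intervals (critical value 2.53 in place of 1.97). Power per regimen falls by about 1 point at 45 v 45 (99.7% to 98.6%). No added patients are needed, because the safety consideration in Section 3.1 already sets 45 active patients per cohort.
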